### **5.6. Criteria for Permanent Discontinuation of Study Drug**

Investigators are encouraged to keep a subject who is experiencing clinical benefit in the study unless significant toxicity puts the subject at risk or routine noncompliance puts the study outcomes at risk. For a complete list of criteria for permanent discontinuation of study treatment, refer to [Section 9.2](#).

Subjects who withdraw for any reason other than those specified in [Section 5.3](#) and [9.2](#) will not be replaced. A Treatment Termination Visit ([Section 8.2.3](#)) and End-of-Treatment Visit ([Section 8.3.1](#)) are required for all subjects except for those subjects who have withdrawn full consent.

## **6. CONCOMITANT MEDICATIONS/PROCEDURES**

Concomitant therapies must be collected from the time of ICF signing or 14 days prior to the first dose, whichever is greater, until 30 days after the last dose of ibrutinib and 90 days after the last dose of MEDI4736.

### **6.1. Permitted Concomitant Medications**

Supportive medications in accordance with standard practice (such as for emesis, diarrhea, etc.) are permitted. Use of neutrophil growth factors (filgrastim and pegfilgrastim) or red blood cell growth factors (erythropoietin) is permitted per institutional policy and in accordance with ASCO guidelines ([Smith 2006](#)). Transfusions may be given in accordance with institutional policy.

Hormonal or bone sparing treatment are permitted with approval of the Medical Monitor.

Short courses ( $\leq 14$  days) of corticosteroid treatment for non-cancer related medical reasons considered unrelated to study treatment (eg, unrelated joint inflammation, asthma exacerbation, rash, antiemetic use and infusion reactions) at doses that do not exceed 100 mg per day of prednisone or equivalent are permitted after discussion with the Medical Monitor. During corticosteroid treatment with  $>10$  mg per day of prednisone or equivalent, MEDI4736 should be held until event resolution to Grade  $\leq 1$  or baseline; thereafter MEDI4736 administration may be resumed at the next scheduled dose. Doses higher than this are permitted only for infusion prophylaxis/reactions or for acute toxicity management.

If corticosteroid treatment for study drug related adverse events with  $>10$  mg per day of prednisone or equivalent is needed, MEDI4736 should be held until the event resolves to Grade  $\leq 1$  or baseline and the Medical Monitor should be contacted. Thereafter, MEDI4736

administration may be resumed at the next scheduled dose (also see [Section 5.5.2.4](#) for Dose Modifications for Adverse Reactions).

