#### **5.5.2.4. Dose Modification for Adverse Reactions**

Refer to [Section 6.1](#) for use of corticosteroids as concomitant medications.

The table below outlines the MEDI4736 Toxicity Management Guidelines.

Immune-Mediated Reactions		
	Dose Modifications	Toxicity Management
Immune-related Adverse Events (Overall Management for toxicities not noted below)	
Drug administration modifications of study drug/study regimen will be made to manage potential immune-related AEs based on severity of treatment-emergent toxicities graded per NCI CTCAE v4.03.
 
In addition to the criteria for permanent discontinuation of study drug/regimen based on CTC grade/severity (table below), permanently discontinue study drug/study regimen for the following conditions:
 
 
• Inability to reduce corticosteroid to a dose of <math>\leq 10</math> mg of prednisone per day (or equivalent) within 12 weeks after last dose of study drug/regimen
 
• Recurrence of a previously experienced Grade 3 treatment-related AE following resumption of dosing.
 
	
It is recommended that management of irAEs follow the guidelines presented in this Table:
 
 
• Subjects should be thoroughly evaluated to rule out any alternative etiology (eg, disease progression, concomitant medications, infections, etc.)
 
• In the absence of a clear alternative etiology, all events should be considered potentially immune related.
 
• Symptomatic and topical therapy should be considered for low-grade (Grade 1 or 2, unless otherwise specified) events
 
• For persistent (greater than 3 to 5 days) low-grade (Grade 2) or severe (Grade <math>\geq 3</math>) events promptly start prednisone PO 1-2mg/kg/day or IV equivalent
 
• If symptoms recur or worsen during corticosteroid tapering (28 days of taper), increase the corticosteroid dose (prednisone dose [eg, up to 2-4 mg/kg/day or IV equivalent]) until stabilization or improvement of symptoms, then resume corticosteroid tapering at a slower rate (<math>\geq 28</math> days of taper)
 
• More potent immunosuppressives – TNF inhibitors (eg, infliximab) – (also refer to the individual sections of the immune related adverse event for specific type of immunosuppressive) should be considered for events not responding to systemic steroids
 
• Discontinuation of study drug is not mandated for Grade 3/Grade 4 inflammatory reactions attributed to local tumour response (eg, inflammatory reaction at sites of metastatic disease, lymph nodes etc.). Continuation of study drug in this situation should be based upon a benefit/risk analysis for that subject.
 

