Grade 1	No dose modification	
Grade 2	
Hold study drug/study regimen dose until Grade 2 resolution to Grade <math>\leq 1</math>
 
 
• If toxicity worsens then treat as Grade 3 or Grade 4
 
• If toxicity improves to baseline then treat at next scheduled treatment date
 
• Study drug/study treatment can be resumed at the next scheduled dose once event stabilizes to grade <math>\leq 1</math> and 5-7 days have passed after completion of steroid taper
 
• Subjects with endocrinopathies who may require prolonged or continued steroid replacement can be retreated with study drug/study regimen on the following conditions: 1) the event stabilizes and is controlled, 2) the subject is clinically
 
	

Immune-Mediated Reactions			
	Dose Modifications		Toxicity Management
		stable as per Investigator or treating physician's clinical judgment, and 3) doses of prednisone are at less than or equal to 10mg/day or equivalent.	
	Grade 3	Depending on the individual toxicity, may permanently discontinue study drug/study regimen. Please refer to guidelines below	
	Grade 4	Permanently discontinue study drug/study regimen  Note: For Grade 3 and above asymptomatic amylase or lipase levels hold study drug/regimen and if complete work up shows no evidence of pancreatitis, may continue or resume study drug/regimen	
Pneumonitis/ Interstitial lung disease (ILD)	Grade of Pneumonitis (CTCAE v 4.03)	Any Grade	
 
Monitor subjects for signs and symptoms of pneumonitis or ILD (new onset or worsening shortness of breath or cough). Subjects should be evaluated with imaging and pulmonary function tests including other diagnostic procedures as described below
 
Initial work-up may include clinical evaluation, monitoring of oxygenation via pulse oximetry (resting and exertion), laboratory work-up and high-resolution CT scan
 

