Grade 1 diarrhea (stool frequency of <4 over baseline per day)	No dose modification	
For Grade 1 diarrhea:
 
 
• Close monitoring for worsening symptoms
 
• Consider symptomatic treatment including hydration, electrolyte replacement, dietary changes (eg, American Dietetic Association colitis diet), and loperamide. Use of probiotics as per treating physician's clinical judgment.
 

Grade 2 diarrhea (stool frequency of 4-6 over baseline per day)	
Hold study drug/study regimen until resolution to Grade <math>\leq 1</math>
 
 
• If toxicity worsens then treat as Grade 3 or Grade 4
 
• If toxicity improves to baseline then treat at next scheduled treatment date
 
• Study drug/study regimen can be resumed at the next scheduled dose once event stabilizes to Grade <math>\leq 1</math> and 5-7 days have passed after completion of steroid taper.
 
	
For Grade 2 diarrhea:
 
 
• Consider symptomatic treatment including hydration, electrolyte replacement, dietary changes (eg, American Dietetic Association colitis diet), and loperamide and/or budesonide
 
• Promptly start prednisone 1 to 2 mg/kg/day or IV equivalent
 
• If not responsive within 3-5 days, consider IV corticosteroids (eg, methylprednisolone IV or equivalent) at 1 to 2 mg/kg/day
 
• If event is not responsive within 3-5 days or worsens despite prednisone at 1-2 mg/kg/day or IV equivalent, GI consult should be obtained for consideration of further workup such as imaging and/or colonoscopy to confirm colitis and rule out perforation, and prompt treatment with IV methylprednisolone 2-4 mg/kg/day started.
 
• If still no improvement within 3-5 days despite 2-4 mg/kg IV methylprednisolone, promptly start immunosuppressives such as (infliximab at 5 mg/kg once every 2 weeks) Caution: Important to rule out bowel perforation and refer to infliximab label for general guidance before using infliximab
 
• Consult study physician if no resolution to <math>\leq</math>Grade 1 in 3-4 days
 
• Once improving, gradually taper steroids over <math>\geq</math>28 days and consider prophylactic antibiotics, antifungals and anti PCP treatment (please refer to current NCCN guidelines for treatment of cancer-related infections [Category 2B recommendation])
 

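### Section 6.1 sets no steroid-taper condition for restarting MEDI4736, the Grade 2 rows of Section 5.5.2.4 do, and neither says which governs

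*Protocol*

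**What the plan says.** **Section 6.1.** For study-drug-related events, if corticosteroid treatment above 10 "mg per day of prednisone or equivalent is needed, MEDI4736 should be held until the event resolves to Grade" ≤1 "or baseline and the Medical Monitor should be contacted". After that its "administration may be resumed at the next scheduled dose (also see" Section 5.5.2.4). The rule depends on the grade of the event. It does not mention whether steroids have been tapered or stopped.

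**Section 5.5.2.4, Grade 2 rows.** Eight rows make restart conditional on the taper: immune-related events overall, pneumonitis, diarrhea, hepatitis, creatinine, rash, endocrinopathy and neurotoxicity. In each, the event must have stabilized at Grade ≤1 "and 5-7 days have passed after completion of steroid taper" (the creatinine row has this in garbled form). The same eight rows also have a return-to-baseline route with no taper condition, typically "If toxicity improves to baseline then treat at next scheduled treatment date". In the pneumonitis row that route is left to the treating physician's judgment, so seven rows have it as a direct instruction.

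**Cross-references.** Section 6.1 points to 5.5.2.4, and 5.5.2.4 opens by pointing back to 6.1 for corticosteroid use. Neither ranks the two.

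**The concern.** Immune-mediated events are a main named risk of MEDI4736 (Section 1.5.3). The table itself provides for relapse while steroids come down: "If symptoms recur or worsen during corticosteroid tapering (28 days of taper), increase the corticosteroid dose". A restart taken from 6.1 can fall in exactly that period. Two sites with the same patient could act differently, each following a stated rule. Safety management, exposure and the immune-event summaries would then depend on which section a site opened. The response-rate hypothesis test does not use these rules.

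**Working it through.** There is no figure in the plan to reproduce. The check sets the texts side by side and then illustrates the timing.

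**Step 1: a Grade 2 event, on prednisone above 10 mg/day, now Grade 1 and not at baseline.**

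| | Section 6.1 | Section 5.5.2.4, Grade 2 rows |
|---|---|---|
| Event grade needed | ≤1 or baseline | ≤1 |
| Taper complete? | not mentioned | yes, plus 5–7 days |
| Other step | contact Medical Monitor | none in this bullet |
| Next dose during taper | permitted | not permitted |

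The return-to-baseline route is not open to this subject, so the table gives one answer and 6.1 another.

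**Step 2: the return-to-baseline route, row by row.** Could it be meant only for subjects not on steroids?

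- Overall, hepatitis, creatinine, rash: steroids come in after persistence, worsening or failed symptomatic treatment, so that reading is possible.
- Endocrinopathy: possible, since isolated hypothyroidism is managed without corticosteroids.
- Neurotoxicity: as laid out, the route sits under sensory neuropathy, which has non-steroid options.
- Pneumonitis: steroids start promptly, but restart is expressly a matter of judgment.
- Diarrhea: the Grade 2 instruction is "Promptly start prednisone 1 to 2 mg/kg/day or IV equivalent", then "Once improving, gradually taper steroids over" at least 28 days. A subject reaching baseline will ordinarily be on steroids or tapering, so the steroid-free reading does not fit.

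**Step 3: illustration of the timing.** Inputs from the Protocol: dosing every 14 days; a wait w of 5 or 7 days; a taper L of at least 28 days where a row states a length. Assumed: k, the days from the start of the taper to Grade ≤1. Let d = 0,…,13 be the days from then to the next scheduled dose.

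- First infusion under 6.1: taper day k + d.
- Extra delay under the post-taper bullet: 14 × max(0, ⌈(L + w − k − d)/14⌉).

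Example: L = 28, w = 5, k = 7, d = 3. Section 6.1 allows day 10. The table needs day 33, and scheduled doses fall on days 10, 24 and 38, so the first is day 38. The formula gives ⌈23/14⌉ = 2, so 28 days.

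With L = 28, over both values of w and all 14 values of d:

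| k (assumed) | Delay, days | 6.1 infusion inside taper (k + d < 28) |
|---|---|---|
| 0 | 28 or 42 | 14 of 14 |
| 7 | 14 or 28 | 14 of 14 |
| 14 | 14 or 28 | 14 of 14 |
| 21 | 0 or 14 | 7 of 14 |
| 28 | 0 or 14 | 0 of 14 |
| 35 | 0 | 0 of 14 |

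The protocol sets no maximum taper. At k = 0 the delay is 42 or 56 days for a 42-day taper, and 56 or 70 days for a 56-day taper. The calculation ignores visit windows and compares 6.1 with the post-taper bullet only.

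**The case against.** The best defense is that the sections divide the work. Section 6.1 concerns concomitant medication, is permissive, requires contact with the Medical Monitor, and refers by title to the dose-modification section. Section 5.5.2.4 sends the reader to 6.1 only for steroid use. A careful site would follow the table, and following the stricter rule satisfies both. Much of this stands, and it keeps the point minor. It does not remove it: 6.1 gives a complete hold-and-resume rule of its own, contact is not approval, and a pointer to look elsewhere as well does not say that the other rule overrides.

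Other controls also limit harm. The table escalates management if toxicity worsens, and it requires permanent discontinuation if steroids cannot be brought to 10 mg/day or less within 12 weeks of the last dose.

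A reader might go further and infer that the table contradicts itself across all these Grade 2 rows. The text does not support that. The two routes have different triggers, full recovery and stabilization at Grade ≤1, and may be two deliberate tiers. Most rows also admit the steroid-free reading in Step 2. The creatinine management bullet on resuming at baseline comes after the taper instruction and can be read as applying once the taper is done.

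A reader might also infer that continued steroids bar retreatment except in endocrinopathy at 10 mg/day or less. The table does not say so: the Grade 3 rash and Grade 3 neurotoxicity rows have no taper condition.

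**Conclusion.** The point holds between sections. For a steroid-treated Grade 2 immune-mediated event that has fallen to Grade 1, 6.1 permits re-infusion during the taper, the Grade 2 rows do not, and no text says which prevails. Within the table there is an ambiguity, not a contradiction, and Grade 2 diarrhea shows it most clearly.

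Severity is minor and confidence moderate. The delay of 0 to 42 days for a 28-day taper rests on assumed values of k. It measures the difference between two rules, not harm to subjects. The primary response-rate test is unaffected.

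**What to change.** 1. In Section 6.1, replace the closing pointer with a statement that, for immune-mediated events, restart of MEDI4736 is governed by the event-specific row of Section 5.5.2.4. Keep the present 6.1 rule for study-drug-related events that are not immune-mediated.
2. In the Grade 2 diarrhea row, state whether the return-to-baseline route applies to subjects who received systemic steroids. Suggested: limit it to those who did not. Grade 3 or 4 diarrhea already means permanent discontinuation, so this does not make the milder event's restart rule the stricter one.
3. Leave unchanged the pneumonitis rules (including Section 11.4.6.2), the Grade 3 rows, the neuromotor rows, the permanent-discontinuation rules and the endocrinopathy exception at 10 mg/day or less. Rewriting every Grade 2 row would be a clinical trade-off. For rash and neurotoxicity it would tighten Grade 2 restart while Grade 3 has no taper condition.

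The cost is a wording change in an amendment and a notice to sites, with no added subjects, visits or procedures. The downside is that some steroid-treated subjects will have infusions delayed. Missed doses are not made up (Section 5.4), so in the illustration a 42-day delay costs 42/14 = 3 of at most 26 doses (Section 1.8.3).

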## **6.2. Medications to Be Used with Caution**

### **6.2.1. CYP3A-inhibitors/Inducers**

Ibrutinib is metabolized primarily by CYP3A4. Avoid co-administration with strong CYP3A4 or moderate CYP3A inhibitors and consider alternative agents with less CYP3A inhibition.

- If a strong CYP3A inhibitor (eg, ketoconazole, indinavir, nelfinavir, ritonavir, saquinavir, clarithromycin, telithromycin, itraconazole, nefazadone, or cobicistat) must be used, reduce ibrutinib dose to 140 mg or withhold treatment for the duration of the inhibitor use. Subjects should be monitored for signs of ibrutinib toxicity.
- If a moderate CYP3A inhibitor (eg, voriconazole, erythromycin, amprenavir, aprepitant, atazanavir, ciprofloxacin, crizotinib, darunavir/ritonavir, diltiazem, fluconazole, fosamprenavir, imatinib, verapamil, amiodarone, or dronedarone) must be used, reduce ibrutinib to 140 mg for the duration of the inhibitor use. Avoid grapefruit and Seville oranges during ibrutinib treatment, as these contain moderate inhibitors of CYP3A (see [Appendix 5](#)).
- No dose adjustment is required in combination with mild inhibitors.

Avoid concomitant use of strong CYP3A inducers (eg, carbamazepine, rifampin, phenytoin, and St. John's Wort). Consider alternative agents with less CYP3A induction (see [Section 5.5.1.2](#)).

A list of common CYP3A inhibitors and inducers is provided in [Appendix 5](#); For further information, please refer to the current version of the [IB](#) and examples of inhibitors, inducers, and substrates can be found at <http://medicine.iupui.edu/clinpharm/ddis/main-table/>. This website is continually revised and should be checked frequently for updates.

### **6.2.2. Drugs That May Have Their Plasma Concentrations Altered by Ibrutinib**

*In vitro* studies indicated that ibrutinib is not a substrate of P-glycoprotein (P-gp), but is a mild inhibitor. Ibrutinib is not expected to have systemic drug-drug interactions with P-gp substrates. However, it cannot be excluded that ibrutinib could inhibit intestinal P-gp after a therapeutic dose. There is no clinical data available. Therefore, to avoid a potential interaction in the gastrointestinal tract, narrow therapeutic range P-gp substrates such as digoxin, should be taken at least 6 hours before or after ibrutinib.

### **6.2.3. Antiplatelet Agents and Anticoagulants**

Warfarin or vitamin K antagonists should not be administered concomitantly with ibrutinib. Supplements such as fish oil and vitamin E preparations should be avoided. Use ibrutinib with caution in subjects requiring other anticoagulants or medications that inhibit platelet function.

Subjects with congenital bleeding diathesis have not been studied. For guidance on ibrutinib and the use of anticoagulants during procedures/surgeries see [Section 6.4](#).

For subjects requiring the initiation of therapeutic anticoagulation therapy (eg, atrial fibrillation), consider the risks and benefits of continuing ibrutinib treatment. If therapeutic anticoagulation is clinically indicated, treatment with ibrutinib should be held and not be restarted until the subject is clinically stable and has no signs of bleeding. Subjects should be observed closely for signs and symptoms of bleeding. No dose reduction is required when study drug is restarted.

### **6.3. Prohibited Concomitant Medications**

Any chemotherapy, anticancer immunotherapy, experimental therapy, or radiotherapy is prohibited while the subject is receiving ibrutinib treatment.

Transfusional support is prohibited for at least 7 days prior to Screening. Pegylated G-CSF (pegfilgrastim) and darbepoetin are prohibited for at least 14 days prior to Screening.

Immunosuppressive medications within 14 days before the first dose of MEDI4736 and throughout the study are prohibited. The following are exceptions to this criterion:

- Intranasal, inhaled, topical corticosteroids, or local corticosteroid injections (eg, intra-articular injection)
- Corticosteroids as pre-medication for hypersensitivity reactions (eg, CT scan pre-medication)
- Corticosteroids given for prevention or treatment of infusion reactions
- Corticosteroids given for acute toxicity management, eg pneumonitis or other immune-related AEs, or non-cancer related medical reasons per guidance in [Section 6.1](#)

The Sponsor must be notified in advance (or as soon as possible thereafter) of any instances in which prohibited therapies are administered.

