	Grade 2  (AST or ALT $>$ 3 to 5 times ULN and/or TB $>$ 1.5-3.0 times ULN)	Hold study drug/study regimen dose until Grade 2 resolution to Grade $\leq 1$ 
 
If toxicity worsens then treat as Grade 3 or Grade 4
 
If improves to baseline then treat at next scheduled treatment date
 
Study drug/study regimen can be resumed at the next scheduled dose once
 
	
For Grade 2 AST or ALT and or TB elevation:
 
 
Regular and frequent checking of LFTs (e.g. every 1-2 days) until elevations of these are improving or resolved.
 
If no resolution to <math>\leq</math>Grade 1 in 1-2 days, discuss with study physician.
 
If event is persistent (<math>>3-5</math> days) or worsens, promptly start prednisone 1-2 mg/kg/day or IV equivalent
 
If still no improvement within 3-5 days, despite 1-2 mg/kg/day of prednisone or IV equivalent, consider additional workup and prompt treatment with IV methylprednisolone 2-4 mg/kg/day started.
 
If still no improvement within 3-5 days despite 2-4 mg/kg/day of IV methylprednisolone,
 

Immune-Mediated Reactions		
	Dose Modifications	Toxicity Management
	
event stabilizes to Grade <math>\leq 1</math> and 5-7 days have passed after completion of steroid taper
	
promptly start immunosuppressives (eg, mycophenolate mofetil). Discuss with study physician if mycophenolate mofetil is not available. Infliximab should NOT be used.
 
 
Once improving, gradually taper steroids over <math>\geq 28</math> days and consider prophylactic antibiotics, , antifungals and anti PCP treatment (please refer to current NCCN guidelines for treatment of cancer-related infections [Category 2B recommendation])
 

 ASCO Educational Book 2015 “Managing Immune Checkpoint Blocking Antibody Side Effects” , by Michael Postow MD

Immune-Mediated Reactions			
	Dose Modifications		Toxicity Management
		absence of any alternative cause iv	
	Grade 4	Permanently discontinue study drug/study regimen	

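### Section 6.3 bans all non-steroid immunosuppressants during the study, yet Section 5.5.2.4 tells investigators to start infliximab or mycophenolate when steroids fail

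*Protocol*

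**What the plan says.** Section 6.3 of the Protocol sets a class-wide ban: "Immunosuppressive medications within 14 days before the first dose of MEDI4736 and throughout the study are prohibited". Four exceptions follow: local or topical corticosteroids, corticosteroid pre-medication, corticosteroids for infusion reactions, and a last one that begins "Corticosteroids given for acute toxicity management, eg pneumonitis or other immune-related AEs" and refers to Section 6.1. The section closes with a reporting duty: "The Sponsor must be notified in advance (or as soon as possible thereafter) of any instances in which prohibited therapies are administered".

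Section 5.5.2.4 holds the MEDI4736 toxicity management table and gives it this status: "It is recommended that management of irAEs follow the guidelines presented in this Table". For Grade 2 diarrhea that has not improved on steroids, the table says "promptly start immunosuppressives such as (infliximab at 5 mg/kg once every 2 weeks". For Grade 2 hepatitis in the same situation it says "promptly start immunosuppressives (eg, mycophenolate mofetil" and forbids infliximab.

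**The concern.** The same class of drug is prohibited in one section and recommended in another. The last exception in Section 6.3 shows that the authors had immune-related adverse events in mind there, but they exempted only the first line of treatment for them. The table's second line, used when steroids do not work, stays under the ban.

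What is at stake is patient safety and clean conduct. The table asks for prompt escalation after 3-5 days without improvement, so an investigator who stops to resolve the contradiction loses time. One who follows the table may have a protocol deviation recorded. Section 9.2 gives a significant protocol deviation as an example of an investigator's reason to stop study treatment, so such a record is not purely clerical, although stopping would remain discretionary.

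**Working it through.** No formula applies and the plan states no figure to reproduce. The check sets the two sections side by side and then looks for any clause that reconciles them.

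**Step 1. Exceptions in Section 6.3.** Four are listed and all four name corticosteroids. Exceptions covering a non-steroid immunosuppressant: 0 of 4.

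**Step 2. Rows of Section 5.5.2.4 that call for a non-steroid agent after steroid failure.**

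| Row | Agent | Study drug |
|---|---|---|
| Diarrhea, Grade 2 | Infliximab | Held, may resume |
| Hepatitis, Grade 2 | Mycophenolate mofetil | Held, may resume |
| Pneumonitis, Grade 3-4 | TNF inhibitor, eg infliximab | Permanently stopped |
| Diarrhea, Grade 3-4 | Infliximab | Permanently stopped |

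Count: 2 + 2 = 4 rows.

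**Step 3. Is the subject still covered by the ban?** In the Grade 2 diarrhea row the dose instruction is "Hold study drug/study regimen until resolution to Grade" 1 or lower, and then "Study drug/study regimen can be resumed at the next scheduled dose once event stabilizes to Grade" 1 or lower, with 5-7 days elapsed after the steroid taper. The Grade 2 hepatitis row has the same structure. These subjects are in the treatment phase on any reading of the ban.

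In the two Grade 3-4 rows the conflict rests on the literal duration of the ban. Section 6.3 limits its ban on chemotherapy, anticancer immunotherapy, experimental therapy and radiotherapy to the time on ibrutinib, but puts no such limit on the immunosuppressant ban. Concomitant therapies are still collected for 30 days after the last ibrutinib dose and 90 days after the last MEDI4736 dose (Section 6). For pneumonitis, Section 11.4.6.2 stops MEDI4736 only, and Section 8.3.2 foresees subjects continuing on ibrutinib alone, so such a subject might still be on treatment. These rows are secondary.

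**Step 4. Rows not counted.** The overall management row only asks that TNF inhibitors be considered. IVIG for neurotoxicity is left out because SAP Section 3.3 summarizes immunoglobulin together with blood supportive products. The management text for Grade 2 pneumonitis and Grade 3 hepatitis is cut in the copy reviewed.

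**Step 5. Does anything else permit these agents?**

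- Section 6.1 allows supportive medication under standard practice and mentions diarrhea, but it names no non-steroid immunosuppressant and does not lift the ban in Section 6.3. Its guidance on immunosuppression concerns corticosteroids.
- Section 5.5.2.4 opens by sending the reader to Section 6.1, for corticosteroid use only.
- The notification sentence in Section 6.3 is a reporting route. It still classes the agents as prohibited.
- The immediate-hazard wording in Section 12.14 concerns changes to study procedures.

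None of these reconciles the two sections.

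**The case against.** The best counter-argument is that a sensible reader would not be misled. The last exception in Section 6.3 leads to Section 6.1, which in turn refers to Section 5.5.2.4, the table that names infliximab and mycophenolate. Section 6.1 also lifts its steroid dose limit for acute toxicity management, which suggests that toxicity care was meant to override general limits. The table is specific on agent and timing, while Section 6.3 is a general list, and most sites would probably follow the table. Neither document says that doing so would be logged as a deviation.

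Part of this stands. Practical harm is likely to be small, and the Grade 3-4 rows are open to a treatment-period reading that would leave only the two Grade 2 rows. But the reference in Section 6.1 concerns holding and resuming MEDI4736 around corticosteroid use and permits no other agent. A reader who has to infer that one section overrides another has been given two conflicting rules.

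A second objection is that the resumption rules in the Grade 2 rows refer only to the steroid taper and do not address a subject still on infliximab or mycophenolate. That is true, but it is a separate gap in Section 5.5.2.4, which the proposed change neither creates nor worsens.

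**Conclusion.** The contradiction is real and should be corrected. It is firm for 2 rows of the table (Grade 2 diarrhea and Grade 2 hepatitis). It extends to 4 rows if the ban is taken literally to continue after study drug stops. No number of affected subjects can be given, because the documents do not report how often immune-related adverse events are steroid-refractory with this combination.

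This is an internal inconsistency in safety wording. It does not bear on the statistical design.

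**What to change.** Add a fifth exception to Section 6.3: *Other immunosuppressants (eg, infliximab, mycophenolate mofetil, IVIG) given for management of immune-related AEs per Section 5.5.2.4.* Leave the four corticosteroid exceptions as they are. The cross-reference keeps the table's rule against infliximab in immune-related hepatitis. Naming IVIG does no harm, since the neurotoxicity rows of the table themselves treat it as immunosuppressive.

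The cost is one line in the next amendment, with no added procedures or patients. The same amendment would be a convenient place to say when MEDI4736 may resume in a subject still receiving a non-steroid agent, but the fix does not depend on it.
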